#### 6.1.2.2 Nausea/Vomiting

The following dose modifications are based on toxicity experienced during a cycle.

- For grade 3 Nausea/Vomiting (despite optimal medical management):
  - First Occurrence: Delay chemotherapy until recovery to grade  $\leq 1$  or baseline, then resume 5-FU and leucovorin, at the same dose level and oxaliplatin and irinotecan with one dose level reduction for all subsequent cycles.
  - Second or More Occurrence: Delay chemotherapy until recovery to grade  $\leq 1$  or baseline, then resume chemotherapy with one dose level reduction for all subsequent cycles. **NOTE**: The dose of leucovorin is not reduced.
- For grade 4 Nausea/Vomiting (despite optimal medical management): Delay chemotherapy until recovery to grade  $\leq 1$  or baseline, then resume chemotherapy with one dose level reduction for all subsequent cycles. **NOTE**: The dose of leucovorin is not reduced.

#### 6.1.2.3 Mucositis

The following dose modifications are based on toxicity experienced at any time during a cycle.

- For grade 3 Mucositis:
  - First Occurrence: Delay chemotherapy until recovery to grade  $\leq 1$ , then resume irinotecan, oxaliplatin, and leucovorin at the same dose level and 5-FU with one dose level reduction for all subsequent cycles.
  - For Second or More Occurrence: Delay chemotherapy until recovery to grade  $\leq 1$ , then resume chemotherapy with one dose level reduction in irinotecan and oxaliplatin for all subsequent cycles. Dose of 5FU is reduced two dose levels for all subsequent cycles). **NOTE**: The dose of leucovorin is not reduced.
- For grade 4 Mucositis: Delay chemotherapy until recovery to grade  $\leq 1$ , then resume chemotherapy with one dose level reduction for all subsequent cycles. **NOTE**: The dose of leucovorin is not reduced.

#### 6.1.2.4 Peripheral Sensory Neuropathy

- For paresthesia/dysesthesia interfering with function and persisting between treatments: decrease oxaliplatin by one dose level for all subsequent cycles.
- For painful paresthesia/dysesthesia or symptoms that interfere with function and ADL, but improve (no longer painful or no longer interfering with ADL) between treatments: decrease oxaliplatin by one dose level for all subsequent cycles.

- For painful paresthesia/dysesthesia or symptoms that interfere with function and ADL that persists between treatments: discontinue oxaliplatin.
- For persistent disabling or life-threatening paresthesia/dysesthesia: discontinue oxaliplatin.
- For pharyngo-laryngeal dysesthesia: increase the duration of oxaliplatin infusion to 6 hours for subsequent cycles.

#### 6.1.2.5 Oxaliplatin-induced pharyngolaryngeal dysesthesias

Should a patient develop oxaliplatin-induced pharyngolaryngeal dysesthesia, her/his oxygen saturation should be evaluated via a pulse oximeter; if normal, an anxiolytic agent may be given and the patient observed in the clinic until the episode has resolved. Following resolution of symptoms, patients may continue/resume oxaliplatin if the reaction is NOT determined to be an allergic reaction.

A table comparing pharyngolaryngodysesthesia to platinum hypersensitivity reactions is presented below.

*Table 1 - Comparison of the Symptoms and Treatment of Pharyngolaryngodysesthesias and Platinum Hypersensitivity Reactions*

Clinical Symptoms	Pharyngo-Laryngeal Dysesthesias	Platinum Hypersensitivity
Dyspnea	Present	Present
Bronchospasm	Absent	Present
Laryngospasm	Absent	Present
Anxiety	Present	Present
O 2 saturation	Normal	Decreased
Difficulty swallowing	Present (loss of sensation)	Absent
Pruritis	Absent	Present
Urticaria/rash	Absent	Present
Cold-induced symptoms	Yes	No
Blood pressure	Normal or increased	Normal or decreased
Treatment	Anxiolytics, observation in a controlled clinical setting until symptoms abate or at the physician's discretion	Oxygen, steroids, epinephrine, bronchodilators; fluids and vasopressors, if appropriate

#### 6.1.2.6 Venous Thromboembolic Events

- For grade 2 or 3 venous thromboembolic event: Continue chemotherapy at the same dose level. Do not use warfarin for therapeutic anticoagulation.
- For grade 4 venous thromboembolic event: Discontinue chemotherapy.

#### 6.1.2.7 Liver Function Tests

- For grade 2 Increased Blood Bilirubin: Skip irinotecan until bilirubin improves to  $\leq$  grade 1.

- For hyperbilirubinemia considered at least possibly related to irinotecan, then resume irinotecan with one dose level reduction for all subsequent cycles.
- For hyperbilirubinemia considered unrelated to irinotecan, resume irinotecan at the previous dose level.
- For grade 3 or 4 Increased Blood Bilirubin: Delay chemotherapy until bilirubin improves to  $\leq$  grade 1. If bilirubin is thought to be due to a chemotherapy drug, then resume that drug at the next lower dose level and the other drugs at the same dose level when total bilirubin improves to  $\leq$  grade 1.
  - For hyperbilirubinemia considered at least possibly related to treatment (any drug) resume chemotherapy with one dose level reduction in suspect drug(s) for all subsequent cycles.
  - For hyperbilirubinemia considered unrelated to treatment (all drugs), resume chemotherapy at the previous dose levels.

#### 6.1.2.7 Allergic Reactions

For grade 2 allergic reactions: Interrupt infusion(s). Manage reaction according to institutional policy. Restart the infusion(s) when symptoms resolve to  $\leq$  grade 1 and pre-treat before all subsequent doses.

For grade 3 or Grade 4 allergic reactions: Discontinue infusion. Manage reaction according to institutional policy. Discontinue chemotherapy.

#### 6.1.2.8 Other non-hematologic toxicities

For all other grade 3 non-hematologic toxicities considered at least possibly related to chemotherapy: Skip the responsible drug(s) until toxicity improves to  $\leq$  grade 1, then resume the responsible drug(s) with one dose level reduction for all subsequent cycles.

For grade 4 non-hematologic toxicities considered at least possibly related to chemotherapy: Discontinue the responsible drug(s).

### 6.2 Radiation Therapy

Uninterrupted treatment is planned. RT will be held on any planned treatment day on which the patient exhibits  $\geq$  Grade 3 gastrointestinal toxicity that is reasonably attributed to pelvic RT. RT may be held until the toxicity resolves to less than Grade  $\leq 2$ , at which point RT may be resumed. The patient will be assessed by a physician once during the course of RT during which any delays, interruptions, or discontinuation of treatment will be determined.

Symptom	CTCAE v 5.0 Criteria for Grading			
	1	2	3	4
Proctitis	Rectal discomfort, intervention not indicated	Symptoms (e.g., rectal discomfort, passing blood or mucus), medical intervention indicated; limiting instrumental ADL	Severe symptoms; fecal urgency or stool incontinence; limiting self care ADL	Life-threatening consequences urgent intervention indicated

Cystitis – noninfective	Microscopic hematuria; minimal increase in frequency, urgency, dysuria, or nocturia; new onset of incontinence	Moderate hematuria; moderate increase in frequency, urgency, dysuria, nocturia or incontinence; urinary catheter placement or bladder irrigation indicated; limiting instrumental ADL	Gross hematuria; transfusion, IV medications or hospitalization indicated; elective endoscopic, radiologic or operative intervention indicated	Life-threatening consequences; urgent radiologic or operative intervention indicated
Enterocolitis	Asymptomatic; clinical or diagnostic observations only; intervention not indicated	Abdominal pain; mucus or blood in stool	Severe or persistent abdominal pain; fever; ileus; peritoneal signs	Life-threatening consequences; urgent intervention indicated
Diarrhea	Increase of <4 stools per day over baseline; mild increase in ostomy output compared to baseline	Increase of 4-6 stools per day over baseline; moderate increase in ostomy output compared to baseline	Increase of >=7 stools per day over baseline; incontinence; hospitalization indicated; severe increase in ostomy output compared to baseline; limiting self care ADL	Life-threatening consequences; urgent intervention indicated

## 7. ADVERSE EVENTS AND REPORTING PROCEDURES

The chemotherapies used on this trial are FDA-approved and are used as part of standard treatment in the US for patients with locally advanced rectal cancer. Therefore, all clinicians recruiting study subjects have considerable experience with this regimen. The toxicity of each specific agent is outlined below. The chemotherapy and radiation used in this clinical trial also represents the standard care for patients with locally advanced rectal cancer

### 7.1 Potential Adverse Events

#### 7.1.1 Capecitabine

COMMON, SOME MAY BE SERIOUS	
In 100 people receiving Capecitabine, more than 20 and up to 100 may have:	

 
• Swelling of the body
 
• Blisters on the skin
 
• Redness, pain or peeling of palms and soles
 
• Pain
 
• Diarrhea, loss of appetite, nausea, vomiting
 
• Sores in mouth which may cause difficulty swallowing
 
• Anemia which may require blood transfusions
 
• Infection, especially when white blood cell count is low
 
• Bruising, bleeding
 
• Feeling of "pins and needles" in arms and legs
 
• Tiredness
 
• Fever
 
	

**OCCASIONAL, SOME MAY BE SERIOUS**

In 100 people receiving Capecitabine, from 4 to 20 may have:

- Blurred vision, dry or itchy eyes
- Muscle spasms, body aches
- Abnormal heartbeat
- Restlessness, irritability
- Swelling of face, fingers and lower legs
- Constipation
- Difficulty with balancing

**RARE, AND SERIOUS**

In 100 people receiving Capecitabine, 3 or fewer may have:

- Allergic reaction which may cause rash, low blood pressure, wheezing, shortness of breath, swelling of the face or throat
- Difficulty speaking, walking or seeing
- Internal bleeding which may cause blood in vomit or black tarry stools
- Damage to the heart
- A new cancer resulting from treatment of earlier cancer

**7.1.2 5-Fluorouracil/Leucovorin****COMMON, SOME MAY BE SERIOUS**

In 100 people receiving 5-Fluorouracil, Leucovorin, more than 20 and up to 100 may have:

- Hair loss
- Redness, pain or peeling of palms and soles
- Rash, increased risk of sunburn, itching
- Diarrhea, nausea, vomiting, loss of appetite
- Difficulty swallowing
- Sores in mouth which may cause difficulty swallowing
- Heartburn
- Headache
- Tiredness

**OCCASIONAL, SOME MAY BE SERIOUS**

In 100 people receiving 5-Fluorouracil, Leucovorin, from 4 to 20 may have:

- Chest pain
- Blood clot
- Belly pain
- Internal bleeding which may cause black tarry stools
- Infection, especially when white blood cell count is low
- Anemia which may require blood transfusions
- Cough, hoarseness
- Bruising, bleeding
- Allergic reaction which may cause rash, low blood pressure, wheezing, shortness of breath, swelling of the face or throat
- Confusion
- Abnormal eye movement, blurred vision, watering eyes
- Discomfort from light
- Swelling, redness, tingling and pain of hands and feet
- Difficulty with balancing

**RARE, AND SERIOUS**

In 100 people receiving 5-Fluorouracil, Leucovorin, 3 or fewer may have:

- Damage to the heart which may cause shortness of breath
- A new cancer resulting from treatment of earlier cancer

**7.1.3. Oxaliplatin****COMMON, SOME MAY BE SERIOUS**

In 100 people receiving Oxaliplatin, more than 20 and up to 100 may have:

- Anemia which may require blood transfusion
- Diarrhea, nausea, vomiting, constipation, loss of appetite
- Tiredness
- Bruising, bleeding
- Infection, especially when white blood cell count is low
- Numbness, tingling or pain, "pins and needles" of the hands, feet, arms and legs
- Tingling or a loss of feeling in your hands, feet, nose, or tightness in throat or jaw, or difficulty swallowing or breathing which may be made worse by exposure to cold
- Pain
- Fever, cough

**OCCASIONAL, SOME MAY BE SERIOUS**

In 100 people receiving Oxaliplatin, from 4 to 20 may have:

- Blood clot which may cause swelling, pain, or shortness of breath
- Abnormal heartbeat which may cause fainting
- Hearing loss
- Problem with eyelid
- Difficulty walking, using your hands, opening mouth, talking, with balance and hearing, smelling, eating, sleeping, emptying the bladder
- Swelling of the body which may cause shortness of breath
- Blockage of the airway which may cause shortness of breath, cough, wheezing
- Bleeding from multiple sites including vaginal bleeding, bleeding of the testis, or bleeding of the brain
- Internal bleeding which may cause black tarry stool, blood in vomit or urine, or coughing up blood
- Sores in throat or mouth which may cause difficulty swallowing
- Swelling and redness at the site of the medication injection
- Liver damage which may cause yellowing of eyes and skin
- Kidney damage which may require dialysis
- Allergic reaction which may cause rash, low blood pressure, wheezing, shortness of breath, swelling of the face or throat
- Weight gain, weight loss, dehydration
- Dizziness, headache
- Changes in taste, voice
- Abnormal body movement including the eye and eyelid
- Inability to move shoulder or turn head
- Muscle weakness
- Scarring of the lungs
- Hair loss, itching, rash, hives

**RARE, AND SERIOUS**

In 100 people receiving Oxaliplatin, 3 or fewer may have:

- Redness, pain or peeling of palms and soles
- A new cancer resulting from treatment of earlier cancer

#### 7.1.4 Irinotecan

##### **COMMON, SOME MAY BE SERIOUS**

In 100 people receiving Irinotecan, more than 20 and up to 100 may have:

- Severe diarrhea
- Constipation, nausea, vomiting
- Infection, especially when white blood cell count is low
- Hair loss
- Loss of appetite, weight loss
- Anemia which may cause tiredness, or may require a blood transfusion
- Fever, pain
- Dizziness, tiredness, weakness
- Cough, shortness of breath
- Sores in mouth
- Rash
- Bruising, bleeding

##### **OCCASIONAL, SOME MAY BE SERIOUS**

In 100 people receiving Irinotecan, from 4 to 20 may have:

- Allergic reaction which may cause rash, low blood pressure, wheezing, shortness of breath, swelling of the face or throat
- Blood clot which may cause swelling, pain, shortness of breath
- Scarring of the lungs

##### **RARE, AND SERIOUS**

In 100 people receiving Irinotecan, 3 or fewer may have:

- A new cancer resulting from treatment of earlier cancer

#### 7.1.5 Radiation Therapy

Expected acute side effects of radiation therapy include:

- Abdominal cramping
- Diarrhea
- Skin erythema
- Dysuria
- Tenesmus
- Leukopenia
- Lymphopenia
- Thrombocytopenia

Late effects of radiation therapy include:

- Increased frequency of bowel movements
- Bowel urgency
- Infertility in women who have not undergone an ovarian transposition
- Early menopause in pre-menopausal women who have not undergone an ovarian transposition
- Vaginal dryness and narrowing

### **7.1.6 Surgical complications**

Surgery is part of the standard treatment of most patients with rectal cancer. The most common complications of surgery for rectal cancer include wound infection, pelvic infection, bleeding, bowel obstruction, vein thrombosis, pneumonia, cardiac arrhythmia, and heart attack.

Long-term side effects include frequent bowel movements, urinary problems, sexual dysfunction, and hernia.

Surgical difficulty will be graded using a 1-10 scale for pelvic fibrosis and technical difficulty.

## **7.2 Adverse Event Reporting**

As Coordinating Center, we will follow guidelines from Stanford's Research Compliance Office and Cancer Clinical Trials Office (CCTO) for defining, identifying, and reporting events as defined below.

### **7.2.1 Serious Adverse Events (SAEs)**

A Serious Adverse Event (SAE) is defined as: Any adverse event that meets any of the following criteria:

- Fatal (i.e., the adverse event actually causes or leads to death)
- Life threatening (i.e., the adverse event, in the view of the investigator, places the patient at immediate risk of death). This does not include any adverse event that had it occurred in a more severe form or was allowed to continue might have caused death
- Requires or prolongs inpatient hospitalization
- Results in persistent or significant disability/incapacity (i.e., the adverse event results in substantial disruption of the patient's ability to conduct normal life functions)
- Congenital anomaly/birth defect in a neonate/infant born to a mother exposed to study drug
- Significant medical event in the investigator's judgment (e.g., may jeopardize the patient or may require medical/surgical intervention to prevent one of the outcomes listed above)

#### **7.2.1.1 Reporting SAEs**

- SAEs should be graded according to the NCI Common Terminology Criteria for Adverse Events, Version 5.0. NCI CTCAE v5 can be downloaded from [http://ctep.cancer.gov/protocolDevelopment/electronic\\_applications/ctc.htm](http://ctep.cancer.gov/protocolDevelopment/electronic_applications/ctc.htm)"

SAEs Grade 3 and above require prompt reporting. Routine SAE Grade 3+ reporting will be to [[contact]](mailto:[contact]). These reports will also be sent to [name] and Stanford Research Staff (Research Nurse or Research Coordinators) with subject line: "SECURE: SHORT FOX STUDY Serious Adverse Event." A Case Report Form (CRF) describing the event must be supplied and can be sent as an attachment to the email. It could be generated from the OnCore entry (as a pdf or

report).

Stanford research staff will notify Stanford IRB via ‘eProtocol’ as per regulatory and institutional guidelines. The SAE may also be forwarded to other Stanford regulatory boards, e.g., DSMC, as applicable.

### **7.2.2 Unanticipated Problems (UPs)**

Per Stanford IRB, UPs are events involving risks to participants or others and must meet ALL 3 criteria below:

- 1. Unexpected:** in terms of nature, severity, or frequency, given (a) the research procedures described in the protocol-related documents, and (b) the characteristics of the subject population being studies; AND
- 2. Related** to participation in the research: or there is a reasonable possibility that the incident, experience, or outcome may have been caused by the procedures involved in the research; or if a device is involved, probably caused by, or associated with the device; AND
- 3. Harmful:** suggests that the research places subjects or others at a greater risk of harm (including physical, psychological, economic, or social harm) than was previously known or recognized.

*UPs generally will warrant consideration of substantive changes in the research protocol or informed consent process/document, or other corrective actions, in order to protect the safety, welfare, or rights of subjects or others. Due to this, UPs will be reported promptly to Stanford IRB following the below guidelines.*

A UP may also be an AE or SAE and can be noted in OnCore.

#### **7.2.2.1 Reporting UPs**

UPs should be entered into OnCore and reported within 24 hours of learning of the event. Reporting can be done via email to Stanford Cancer Clinical Trials Office (CCTO) at [[contact]](mailto:[contact]), copying [name] and Stanford research staff (Research Nurse or Research Coordinators), with subject line: “SECURE: SHORT FOX STUDY Unanticipated Problem.” A Case Report Form (CRF) describing the event must be supplied and can be sent as an attachment to the email. It could be generated from the OnCore entry (as a pdf or report).

Stanford research staff will notify Stanford IRB via ‘eProtocol’ as per regulatory guidelines. The UP may also be forwarded to other Stanford regulatory boards, e.g., DSMC, as applicable.

SAE and UP Reporting Requirements				
Hospitalization	Grade 1	Grade 2	Grade 3	Grade 4/5
Hospitalization≤ 24 hrs	UP's within 24 hours	UP's within 24 hours	Report SAE promptly, and UP within 24 hours	Report SAE promptly, and UP within 24 hours
Hospitalization≥ 24 hrs	UP's within 24 hours	UP's within 24 hours	Report SAE promptly, and UP within 24 hours	Report SAE promptly, and UP within 24 hours

SAE Definition: Fatal, life threatening, requires hospitalization or prolongs hospitalization, results in persistent or significant disability, causes congenital anomaly/birth defect or significant medical event.
 
Unexpected Problem (UP) Definition: Unexpected in terms of nature, severity, or frequency. Related to participation in the research. And Harmful suggesting that the research places subjects or others at a greater risk of harm.
 
To report all UP's and SAEs Grade 3 and above: 1) Report to Stanford IRB via eProtocol 2) Enter the event into OnCore, 3) send email to [name] and Clinical Trial Manager with the subject line: "SECURE: SHORT FOX STUDY Serious Adverse Event" and 4) Include Case Report Form describing the event and submit follow up reports for the resolution of the event. For any questions regarding whether an event is an SAE or a UP, please email Protocol Director and Clinical Trial Manager.
 
(Protocol Director) [name]: [contact]  Clinical Trial Manager: [contact]
				

### 7.2.3. Adverse Events (AEs) and AE Monitoring

An AE is defined as any untoward medical occurrence in a clinical investigation subject, regardless of causal attribution.

All AEs should be graded according to the NCI Common Terminology Criteria for Adverse Events, Version 5.0, available at <http://ctep.cancer.gov/reporting/ctc.html>.

AEs should be:

- Assessed at each consultation or follow-up visit,
- Assessed during each chemotherapy cycle (prior to infusion is acceptable), and
- Recorded in patient's medical chart using a Smartphase

Laboratory tests (CBC with differential and CMP) should also be obtained with each chemotherapy administration, and abnormal values also noted indicating AE Grade if applicable. For those patients who choose to receive chemotherapy locally, they will have a televisit, over a secure server, before every cycle where their Stanford treating physician will review and assess any adverse events.

AEs should also be:

- Reported to Stanford as per protocol guideline and upon request
- Noted in patient study charts and binder
- Entered into REDCap

AEs in REDCap should remain current and may be requested by Stanford for study renewals, audits, reports, analyses or other submissions for Stanford IRB, SRC, or DSMC. AEs may also be reviewed by members of the study monitoring group in meetings, audits, and/or site visits.

Updates and outcomes of AEs, SAEs, UPs, and deviations may take place during teleconferences or more frequently as needed.

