## PROTOCOL SYNOPSIS

TITLE	Phase II Trial of Organ Preservation Program Using Short-Course Radiation and FOLFOXIRI for Rectal Cancer (SHORT-FOX)
STUDY PHASE	Phase II
INDICATION	Treatment
INVESTIGATIONAL PRODUCT OR PROCEDURE	Organ preservation approach using short course radiation followed by FOLFOXIRI for patients with non-metastatic, >T2N0 or low T2N0 rectal cancer
PRIMARY OBJECTIVE	To assess clinical complete response of an organ preservation approach using short course radiation followed by intensified chemotherapy
SECONDARY OBJECTIVES	To assess safety in all enrolled patients, local regrowth rate and other cancer specific outcomes (disease-free survival, colostomy-free survival and overall survival), longitudinal health-related quality of life of this organ preservation approach
TREATMENT SUMMARY	Patients will undergo short-course radiation followed by 4 months of FOLFOXIRI. Those who achieve a clinical complete response will be considered for organ preservation approach. All other patients will receive standard of care total mesorectal excision (TME).
SAMPLE SIZE	37 patients
STATISTICAL CONSIDERATIONS	
Sample Size Calculation: We plan to use an optimal Simon 2 stage design and enroll 37 patients with an interim analysis at 17 patients for futility.
 
Primary Endpoint: Clinical complete response assessed 8 (+/-4) weeks after completion of chemotherapy.
 
Secondary Endpoints: Toxicity, local regrowth rate, disease-free survival, colostomy-free survival, and overall survival assessed until study completion.
 
Exploratory Endpoint: Health-related quality of life assessed until study completion.

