micturition symptoms, and sexual function compared to sphincter-sparing surgery, 50-90% of patients who undergoing sphincter-sparing surgery will have bowel dysfunction, including low anterior resection syndrome which is characterized by clustering stools, soiling and fecal incontinence.

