## **4. TREATMENT PLAN**

### **4.1 Pretreatment Studies**

The following will be completed after enrollment and before treatment begins

- HRQOL
- ctDNA
- AE Evaluation

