#### **4.2.5 Follow-Up Schedule (Time 0 = assessment of primary outcome)**

Patients who achieve cCR and are candidates for organ preservation per multidisciplinary review will undergo surveillance per protocol schedule. If tumor shows near complete response, patient may continue to be observed until the next evaluable timepoint.

Additional scans and/or other tests may be performed and will be based on the clinical judgment of the treating physician.

Patients who are not candidates for organ preservation will proceed with TME. These patients will not proceed with the organ preservation surveillance schedule and instead be followed for cancer-specific outcomes (disease-free survival, colostomy-free survival and overall survival) per standard of care as directed by the treating physician. They will be assessed for AEs and health-related quality of life per Study Calendar.

For patients who achieve cCR and are on surveillance schedule, if suspicion of local regrowth (non-resolving residual abnormality that appears to increase in size or appears more suspicious in appearance or palpation, or imaging characteristics concerning for progression), patient will undergo a biopsy or a transanal full-thickness excision (TAE) if deemed appropriate to confirm. If biopsy is positive, patients will be managed per standard of care as directed by the treating physician.

Patients who pursue treatment for disease progression while on study will continue to be followed for OS, but discontinue routine AE assessment and QOLs, and follow-up with their treating physicians per standard of care.

After 2 years, all patients who initiated treatment on the protocol will be off study and followed for survival only. In general, patients who opt for organ preservation are recommended to continue to undergo surveillance years 3-5 as per below:

Recommend surveillance off study during years 3-5:

- Every 3-6 months
  - Exam and sigmoidoscopy
- Every 6 months
  - MRI pelvis and CT chest every 6 months

Follow-up PET/CTs or PET/MRI (preferred) are optional at any follow-up point, as per treating physician.

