## 9. STUDY CALENDAR

Activity	Pre-study (to be performed within 45 days of enrollment unless otherwise specified)	RT	Chemo	Primary Outcome Assessment 8 (+/- 4) weeks after Chemo (Time 0)	Follow-up after Time 0 g		
					Every 3 months	Months 3, 6, 12, 18, 24	Months 6, 12, 18, 24
Pregnancy Test a	X						
Biopsy within 180 days of enrollment	X			X e	X e		
Clinical Exam with DRE b	X		X d	X	X		
Procto/Sigmoidoscopy within 90 days of enrollment	X		X d	X	X		
CT chest/abdomen/pelvis c	X		X d	X			X
MRI pelvis	X		X d	X		X	
Labs-CBCD, CMP, CEA	X		X i	X			X
ECOG	X						
HRQOL	X j			X			X f
PET/MRI or FDG-PET c	X			X			
AE evaluation	X j	X	X	X L	X f		
ctDNA	X j	X k		X		X h	

aNegative pregnancy test by urine, for women non-post-menopausal as defined in Appendix.

bDRE may be deferred for clinical reasons, as determined by treating physician.

cMRI abdomen can substitute for CT abdomen/pelvis per physician discretion; PET imaging is *optional*. PET/MRI is preferred.

dRestaging after 8 (+/-4) weeks of chemotherapy. Procto/sigmoidoscopy and CT CAP can be omitted per physician discretion.

eIf biopsy is needed to rule out residual or progressive tumor, per the discretion of the surgeon

fAfter TME, patients will leave surveillance schedule but continue to receive HRQOLs, and be assessed for treatment-related AEs

gFollow-up appointments and activities 2 weeks before and 2 weeks after each timepoint are permitted, and may be completed virtually.

hAmong only those managed with organ preservation

iCEA does not need to be collected; pre-study CBCD, CMP may suffice for cycle 1 Day 1 chemo labs

jActivities to be done after enrollment and before treatment begins

kctDNA will be collected following completion of RT

LAn additional AE evaluation may be scheduled up to 3 months after completion of chemotherapy if needed

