### **12.5.2 Analysis Plan**

For the toxicity outcome, we will calculate the proportion of patients meeting our definition of toxicity. In addition, we will present the frequency and percent of other adverse events reported in the study.

Local regrowth rate will be calculated as the proportion of patients with local regrowth based on the secondary analysis population. The local regrowth rate and its 95% confidence interval will be calculated.

Disease-free survival is defined as the time from start of RT therapy to date of progression or death due to any cause. If a subject is not known to have progressed or died, then DFS will be censored at the latest date the subject was known to be alive or disease-free (on or before the cut-off date). The DFS distribution will be estimated using the Kaplan-Meier method, and the Kaplan-Meier curves, medians and 95% confidence intervals of the medians will be presented.

Colostomy-free survival distribution will be estimated using the Kaplan-Meier method, and the Kaplan-Meier curves, medians and 95% confidence intervals of the medians will be presented.

OS is defined as the time from start of RT therapy to date of death due to any cause. If a subject is not known to have died, then OS will be censored at the latest date the subject was known to be alive (on or before the study end date). The OS distribution will be estimated using the Kaplan-Meier method, and the Kaplan-Meier curves, medians and 95% confidence intervals of the medians will be presented.

For the HRQOL measures, we will calculate the mean and standard deviations of each of the individual indices at baseline and every 3 months during the duration of the study; we will graphically depict scores at each time point. In addition, we will calculate the difference of the QoL scores at the baseline, time of cCR, and last follow up date and report summary statistics.

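### The descriptive adverse-event table pools two capture rules after TME and does not separate pre-treatment findings; the defined toxicity outcome and toxicity rule are not biased by this

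*Combined protocol and SAP*

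**What the plan says.** The protocol synopsis lists as a secondary objective "To assess safety in all enrolled patients". Several sections then set the scope of adverse-event (AE) capture.

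- **Section 7.2.3** gives the general definition: "An AE is defined as any untoward medical occurrence in a clinical investigation subject, regardless of causal attribution". AEs are to be "Assessed at each consultation or follow-up visit", with no distinction by pathway.
- **Section 9, Study Calendar, footnote f**, attached to the three-monthly AE evaluation, reads: "After TME, patients will leave surveillance schedule but continue to receive HRQOLs, and be assessed for treatment-related AEs".
- **Section 4.2.5** says of patients who go to TME: "They will be assessed for AEs and health-related quality of life per Study Calendar". It sets no scope of its own and refers back to the calendar. It also ends routine AE assessment for patients who are treated for progression.
- **Section 4.1** lists "AE Evaluation" among the activities between enrollment and the start of treatment; calendar footnote j says the same.
- **Section 12.5.2** plans the proportion of patients meeting the toxicity definition, and adds: "we will present the frequency and percent of other adverse events reported in the study". Section 12.5.1 gives one population for toxicity, the primary analysis set, covering both pathways.

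The defined safety measures are narrower. Section 10.2 counts toxicity at least possibly attributed to treatment, up to 3 months after radiotherapy (RT) and chemotherapy. Section 12.2 counts non-hematologic grade 4 or higher toxicity with the same attribution threshold, and 12.7 applies that count to the final decision.

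**The concern.** Footnote f and 7.2.3 give different scopes for the same visits. A patient on organ preservation is assessed for every event; a patient who has had TME is, on the calendar's wording, assessed for treatment-related events. The filter acts at collection, so an event judged unrelated after TME may never be recorded and cannot be re-attributed later. It is also unclear what the filter keeps. Section 4.2 describes treatment as RT followed by chemotherapy, the synopsis treatment summary includes TME, and 7.1.6 lists surgical complications among potential adverse events. Two coordinators could handle the same postoperative event differently.

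The second gap is at the start. A pre-treatment evaluation is collected, but nothing in 12.5.2 limits the table to events that begin or worsen once treatment starts. Symptoms of the rectal tumour itself could be listed as AEs.

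What is at stake is the reading of one descriptive table. A low frequency after TME could mean fewer events or a narrower search, and the reader could not tell which.

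**Working it through.** **1. The plan's own safety figures.** Inputs from 12.2: stop if 7 or more of 17 have toxicity; unacceptable if 14 or more of 37. With X1 the stage 1 count:

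- Early stop = P(X1 ≥ 7), n = 17.
- Overall rejection = early stop + Σ over x = 0 to 6 of P(X1 = x) × P(X2 ≥ 14 − x), X2 from n = 20.
- True rate 25%: early stop 10.7%, reject 13.2% (stated 11% and 13%).
- True rate 40%: early stop 55.2%, reject 74.0% (stated 55% and 74%).

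The figures reproduce. They depend on attributed events only.

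**2. Can the narrowing reach the 10.2 outcome?** That window closes about 13 weeks after RT and chemotherapy. TME follows the response assessment at week 4 to 12, so at most 13 − 4 = 9, 13 − 8 = 5 or 13 − 12 = 1 weeks of the window can fall after TME. Treatment-related events remain in scope then. The first three-monthly visit comes no earlier than week 4 + 13 − 2 = 15 (using the two-week allowance in footnote g), after the window has closed.

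**3. How many patients are under the narrower rule after Time 0?** Assume every patient without clinical complete response (cCR) has TME and completes 8 three-monthly evaluations to month 24.

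- cCR 40%: 37 × 0.6 = 22.2 patients; × 8 = 177.6 of 296 evaluations (60%).
- cCR 20%: 37 × 0.8 = 29.6 patients; × 8 = 236.8 of 296 evaluations (80%).

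These are upper bounds: 4.2.5 lets near-complete responders continue under observation and stops routine AE assessment after treatment for progression. They are shares of visits, not estimates of bias.

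**4. What unequal capture could do to the table.** The documents give no rate of unrelated events. Assume a constant monthly risk r over 24 months, and that no unrelated event is recorded in the TME group. Proportion with an event under full capture = 1 − (1 − r)^24. Pooled proportion recorded = organ-preservation share × that value.

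| r per month | Full capture | Recorded, 20% organ preservation | Recorded, 40% organ preservation |
|---|---|---|---|
| 1% | 21% | 4% | 9% |
| 2% | 38% | 8% | 15% |
| 5% | 71% | 14% | 28% |

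**5. Events that hinge on the meaning of treatment.** Section 2.1 states that "50-90% of patients who undergoing sphincter-sparing surgery will have bowel dysfunction". Applied to all TME patients: 22.2 × 0.5 = 11.1 to 29.6 × 0.9 = 26.6. This is a loose upper bound. The rate is for sphincter-sparing surgery only, and 7.1.5 lists bowel frequency and urgency as late radiation effects, so many such events could be recorded on either reading.

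**6. Pre-treatment findings.** No rate is given. If 20% to 60% of patients had at least one (an assumption), 37 × 0.2 = 7.4 to 37 × 0.6 = 22.2 patients could enter the table before the first fraction.

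**The case against.** A reader might infer that the safety objective itself is biased. The documents do not support that. Sections 10.2 and 12.2 require at least possible attribution in every patient, whatever the pathway, and footnote f keeps treatment-related events. Symptoms present before the first fraction cannot be caused by treatment, so they do not belong in those counts either. This stands.

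It can also be said that footnote f does not contain the word only, whereas footnote h does when it means to restrict, and that 4.2.5 speaks of AEs without a qualifier. That makes the narrow reading less than certain, but 4.2.5 defers to the calendar, and the calendar names treatment-related events. The conflict with 7.2.3 remains.

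Other mitigation is real. Serious adverse event reporting in 7.2.1 is not limited by pathway or attribution. Quality-of-life instruments, including bowel function, continue after TME. The baseline data needed for a new-or-worsened rule will exist; only the rule is missing. The grading table in 6.2 supports the radiation-hold rule and is not an analysis definition; its diarrhea row is expressed relative to baseline, though its proctitis row is not. No comparison of AEs between pathways is planned, so a split by pathway is needed only to make the table readable.

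**Conclusion.** The inconsistency is in the text and affects the table of other adverse events in 12.5.2. If the sections are followed as written, all-cause percentages after Time 0 are understated for TME patients, and the total may include findings that predate treatment. The size is unknown: up to 22 to 30 of 37 patients are exposed to the narrower rule, and the table of illustrative rates above shows how far pooled percentages could fall. Both rest on the stated assumptions.

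The toxicity outcome and the toxicity stopping and decision rule are not biased by the narrowing. This assumes that treatment-related in footnote f is read at the same at-least-possible threshold as 10.2, which should be stated. Whether a severe surgical complication counts as toxicity under 12.2 is also not stated; that follows from the undefined term, not from reduced capture. No boundary or sample size changes. Severity is minor and confined to descriptive safety reporting.

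**What to change.** 1. Reconcile footnote f with 7.2.3 and 4.2.5 so that one AE scope applies in both pathways. State whether treatment includes TME by recording attribution separately to RT, chemotherapy and surgery, using the at-least-possible threshold of 10.2.
2. In 12.5.2, tabulate AEs that start on or after the first RT fraction, or whose CTCAE grade rises from the pre-treatment evaluation on or after it, by worst grade per patient. Show events up to Time 0 for all patients, and events after Time 0 separately for organ preservation and TME. Note that routine AE assessment stops for patients treated for progression (4.2.5). List pre-treatment findings separately.

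The cost is a footnote, a short addition to 12.5.2 and slightly more AE data entry after TME. The visits and the pre-treatment evaluation are already planned.
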